#### Mood:

- Depression short form - is component of the Neurol-QOL (Quality of Life in Neurological Disorders) Measurement System, which is a collaborative effort of the National Institute of Neurological Disorders and Stroke and a number of partnering institutions. This measurement system was designed to be responsive to the needs of researchers in a variety of neurological disorders and to facilitate comparisons of data across clinical trials in different diseases. The short form is comprised of 8 items that were selected from the respective item bank. Items have five response options (e.g., 1=Never, 2=Rarely, 3=Sometimes, 4=Often, 5=Always). Respondents generally can answer 5 questions per minute.
- Emotional and behavioral dyscontrol short form - is component of the Neurol-QOL Measurement System, which is a collaborative effort of the National Institute of Neurological Disorders and Stroke and a number of partnering institutions. This measurement system was designed to be responsive to the needs of researchers in a variety of neurological disorders and to facilitate comparisons of data across clinical trials in different diseases. The short form is comprised of 8 items that were selected from the respective item bank. Items have five response options (e.g., 1=Never, 2=Rarely, 3=Sometimes, 4=Often, 5=Always). Respondents generally can answer 5 questions per minute.

#### Fatigue:

- Fatigue Severity Scale (FSS) - is a self-report 9-item questionnaire with questions related to how fatigue interferes with certain activities and rates its severity. The items are scored on a 7 point scale with 1= strongly disagree and 7= strongly agree. The minimum score =9 and maximum score possible =63. Higher the score= greater fatigue severity.

#### Pain:

- Pain Intensity 3a short form and Pain Interference 4a short form - are components of the Patient Reported Outcome Measurement Information System (PROMIS), which was developed by the NIH to provide a standardized metric for measuring physical, mental, and social health across chronic diseases. PROMIS instruments were developed using item response theory, and have been tested in more than 20,000 individuals drawn from the general US population. The Pain Intensity instrument assesses how much a person hurts. The Pain Interference instrument measures the self-reported consequences of pain on relevant aspects of one's life. This includes the extent to which pain hinders engagement with social, cognitive, emotional, physical, and recreational activities. Each question has five response options ranging in value from one to five.

#### Impulsivity:

- Impulsive-Compulsive Disorders in Parkinson's Disease-Rating Scale (QUIP-RS) is a rating scale designed to measure severity of symptoms and support a diagnosis of impulse control disorders and related disorders in PD. QUIP-RS has 4 primary questions (pertaining to commonly reported thoughts, urges/desires, and behaviors associated with ICDs), each applied to the 4 ICDs (compulsive gambling, buying, eating, and sexual behavior) and 3 related disorders (medication use, punning, and hobbyism). It uses a 5-point Likert scale (score 0-4 for each question) to gauge the frequency of behaviors, and instructs patients to answer questions based on behaviors that occurred in the preceding 4 weeks (or any 4-week period in a designated time frame). Scores for each ICD and related disorder range from 0 to 16, with a higher score indicating greater severity (ie, frequency) of symptoms. The total QUIP-RS score for all ICDs and related disorders combined ranges from 0 to 112. [Weintraub D, et al. 2012]

#### Suicidality:

- The Columbia-Suicide Severity Rating Scale (C-SSRS) is a suicidal ideation rating scale. It rates an individual's degree of suicidal ideation on a scale, ranging from "wish to be dead" to "active suicidal ideation with specific plan and intent." The scale identifies behaviors which may be indicative of an individual's intent to commit suicide. The C-SSRS has been found to be reliable and valid in the identification of suicide risk in several research studies.

#### Motor & non-motor PD signs:

- Movement Disorder Society Unified Parkinson Disease Rating Scale (MDS-UPDRS)- The MDS UPDRS has four parts: Part I (non-motor experiences of daily living), Part II (motor experiences of daily living), Part III (motor examination) and Part IV (motor complications). Part I has two components: IA concerning a number of behaviors that are assessed by the investigator with all pertinent information from patients and caregivers and IB that is completed by the patient with or without the aid of the caregiver, but independently of the investigator. It can, however, be reviewed by the rater to ensure that all questions are answered clearly and the rater can help explain any perceived ambiguities. Part II is designed to be a self-administered questionnaire like Part IB, but can be reviewed by the investigator to ensure completeness and clarity. Part III has instructions for the rater to give or demonstrate to the patient; it is completed by the rater. Part IV has instructions for the rater and also instructions to be read to the patient. This part integrates

patient-derived information with the rater's clinical observations and judgments and is completed by the rater. Rater involvement time for administering the MDS-UPDRS is estimated to require less than 10 min for the interview items of Part I, 15 min for Part III, and 5 min for Part IV, resulting in an equivalent rater time investment to the original scale and meeting the 30-min goal.

- Unified Dyskinesia Rating Scale (UDysRS) is developed to evaluate involuntary movements often associated with treated Parkinson's disease. There are two primary sections: Historical [Part 1 (On-Dyskinesia) and Part 2 (Off-Dystonia)] and Objective [Part 3 (Impairment) and Part 4 (Disability)]. On-Dyskinesia refers to the choreic and dystonic movements described to the patient as "jerking or twisting movements that occur when your medicine is working." Off-Dystonia should be described to the patient as "spasms or cramps that can be painful and occur when your Parkinson's disease medications are not taken or are not working."

**Restless Legs Syndrome:**

- International Restless Legs Syndrome Study Group Rating Scale for restless legs syndrome (IRLS): IRLS is a ten-question instrument for measuring severity of restless legs syndrome (RLS). The scale reflects subjective assessment of the primary features (reflected in questions 1 through 3 and 6 of the scale), intensity and frequency of the disorder (questions 7 and 8 of the scale) and associated sleep problems (reflected in questions 4 and 5 of the scale). The scale also includes questions which probe the impact of symptoms on the patients' mood and daily functioning (question 9 and 10 of the scale). Each question has a set of five response options graded from no RLS or impact (score=0) to very severe RLS or impact (score=4). This produced a total scale whose overall score could range from 0 to 40. IRLS sum score and subscales (symptoms in questions 1,2,4, and 6 through 8; symptoms impact in questions 5, 9 and 10) at every time point will be recorded. Item 3 is used for the total score for overall RLS severity.

**REM Sleep Behavior Disorders:**

- REM sleep behavior disorder screening questionnaire (RBDSQ) – is a 10-item, patient self-rating instrument assessing the subject's sleep behavior with short questions that have to be answered by either "yes" or "no". Items 1 to 4 address the frequency and content of dreams and their relationship to nocturnal movements and behavior. Item 5 asks about self-injuries and injuries of the bed partner. Item 6 consists of four sub items assessing nocturnal motor behavior more specifically, e.g., questions about nocturnal vocalization, sudden limb movements, complex movements, or bedding items that fell down. Items 7 and 8 deal with nocturnal awakenings. Item 9 focuses on disturbed sleep in general and item 10 on the presence of any neurological disorder. The maximum total score of the RBDSQ is 13 points.

4. By assessing the proportion of subjects that drop out of the study due to study drug intolerance.

**Secondary Specific Aim:** To examine the effect of CBD on severity & duration of tremor and other conditions that occur in PD.

**Secondary Outcome Measures:**

The effect of CBD on tremor is measured by the change from baseline to the end of treatment phase (week 4) change in total of scores on items 3.17 and 3.18 in part III of the MDS-UPDRS in the ON state (when anti-PD medication is working). Item 3.17 is rest tremor amplitude. Extremity ratings range from 0: Normal, No tremor to 4: Severe, >10 cm in maximal amplitude. Lip/Jaw ratings are similar but smaller amplitudes. Item 3.18 is constancy of rest tremor: 0 (no tremor) to 4 (present >75% of the exam).

The effect of CBD on other conditions that occur in PD, cognition, anxiety, psychosis, sleep, daytime sleepiness, mood, fatigue, pain, impulsivity, other motor and non-motor PD signs, restless legs syndrome and REM sleep behavior disorder, are measured by the same standardized tools used for safety and tolerability assessments (listed above). The effect of CBD are also measured by Clinical Global Impression (CGI) and Patient Global Impression-improvement (PGI-I) and Change (PGI-C). CGI is a 3-item observer-rated scale that measures illness severity (CGIS), global improvement or change (CGIC) and therapeutic response. The CGI is rated on a 7-point scale, with the severity of illness scale using a range of responses from 1 (normal) through to 7 (amongst the most severely ill patients). CGI-C scores range from 1 (very much improved) through to 7 (very much worse). Treatment response ratings should take account of both therapeutic efficacy and treatment-related adverse events and range from 0 (marked improvement and no side-effects) and 4 (unchanged or worse and side-effects outweigh the therapeutic effects). Each component of the CGI is rated separately. PGI-I is a global index that may be used to rate the response of a condition to a therapy (transition scale). It is a simple, direct, easy to use scale that is intuitively understandable to clinicians. PGI-C is rated on a 7-point scale, evaluating all aspects of patient health and determining if there has been an improvement or not.

## **Stage 2: Randomized, Controlled Trial**

**Primary Specific Aim:** To evaluate the safety and tolerability of CBD, in the form of Epidiolex, in PD.

**Primary Outcome Measures:** The primary objective, to evaluate the safety and tolerability of CBD in PD is assessed in 4 ways:

1. By examining and comparing the frequency of study-related adverse events at each dose level between the two groups (treatment vs. placebo). Adverse events are measured by assessments at study visits and by the standardized phone script administered at each dose level (as in Stage 1).
2. By monitoring and comparing vital signs, orthostatic blood pressures, physical exam, EKG and labs (hematology, complete metabolic profile, and urinalysis) between the two groups. These are collected during study visits.
3. By conducting and comparing standardized assessment tools on cognition, anxiety, psychosis, sleep, daytime sleepiness, mood, fatigue, pain, impulsivity, suicidality, and motor and non-motor PD signs, restless legs syndrome, REM sleep behavior disorder and quality of life. These are the same tools used in the Stage 1 safety and tolerability evaluation, except that a more detailed cognitive assessment, an additional motor test and measures of quality of life are done. These are collected during study visits. The change from baseline to 10th day of 5 mg/kg/day (low dose analysis) and from baseline to the maximum tolerated or targeted dose is compared. The additional tools that are

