#### Dose escalation strategy:

In each of the two 7-week periods, study product (CBD or placebo) will be started at 5 mg/kg/day and increased as tolerated to a maximum weight-adjusted target dose that is determined as a result of the Stage 1 study. The dose escalation strategy is the same as in Stage 1 for each treatment phase, except that subjects will take 5 mg/kg/day for 10 -15 days, and have a study visit before increasing further. The reason for a range of 10-15 days instead of exactly 10 days is to allow for some flexibility in getting subjects in for the study visit. Then the dose is escalated at 3-day intervals (with 5 mg/kg/day increased each interval) until the subject reaches the maximum target dose or experiences intolerable adverse effects, in which case the dose will be dropped to the last tolerated dose. Tolerability will be assessed on the third day of each dose and the subject is instructed whether or not to change the dose on the next day. The maximal tolerated dose is the dose at which 5 mg/kg/day higher was not tolerated on two trials. When subject achieves the maximal tolerated dose or the maximum targeted dose, they will maintain that dose for 28 +/-4 days.

Urine collection, storage and transfer for cannabis and metabolites test protocol is as described in Stage 1.

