#### **C.5 Randomization and drug dispensation:**

Patients who consent will be stratified by age (45 – 60 and 61-78) and disease severity (H&Y 1 – 2.5, 3 – 5) and divided into blocks of a few patients each, depending on order of recruitment. Equal numbers from each block will be assigned to each of two sequence groups. One group will receive the control first and the treatment second, and the other group will receive the treatment first and the control second. Since all subjects receive both treatments randomization and stratification are less critical than in studies with fixed treatment groups, unless order effects are important or an expectedly large number of patients drop out.

The study drug, Epidiolex, and matching placebo will be provided by GW Pharmaceuticals. GW will ship the drug according to British and US regulations. Initially enough study drug will be provided for the Stage 1 open label study, and replenishment shipments will follow. [name], the PI, will obtain a Schedule 1 license and all procedures of drug handling will be according to DEA specifications. Briefly, designated study personnel will receive the study drug, store it, measure and label it ([name] and her fellow) and dispense to the subject (study coordinator).

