#### **F. Data Analysis Plan:**

Intention to treat concept is followed. In order to minimize data entry errors a double data entry system will be used.

If study subject agrees, the de-identified data would be shared within CDPHE Marijuana grantee consortium for future research.

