## **Stage 2: Randomized Controlled Trial**

For the RCT the analysis will be performed in accordance with the analysis plan devised prior to unblinding. Baseline variables will be examined for equality between the two sequence groups. The primary, secondary and exploratory outcomes will be analyzed as below for both the low dose (5 mg/kg/day) and highest tolerated dose.

Primary Specific Aim: To evaluate the safety and tolerability of CBD, in the form of Epidiolex, in PD.

The primary outcome is safety and tolerability and will be assessed in 4 ways:

1. Frequency of study-related adverse events at each dose level collected at standardized phone script administration and at study visits. Analysis (frequency of study-related adverse events at each dose level in the two groups, treatment vs. placebo) will be mostly descriptive, and proportions and confidence intervals will be calculated. Contrasts involving repeated measures on the same subjects can be tested with McNemar's test (for two correlated proportions) or GEE models/GLMMs. Contrasts for independent data can be tested with standard two sample proportions test and with GLMs. Proportions, logistic regression, and relative risk regression can be applied to binary outcomes over a fixed period of time, and Poisson models can be applied to counts or events over time.
2. Vital signs, orthostatic blood pressures, physical exam, EKG and labs (hematology, complete metabolic profile, urinalysis) during study visits. For vital signs and labs, data will be analyzed as a simple two-period crossover trial. Means and confidence intervals will be presented for each group \* treatment, and for the change scores in each group. A two sample T-test will compare the means of the two groups, those in the CBD-placebo group vs. those in the placebo-CBD group, on the change scores between period 1 to period 2. The difference between the means of the two group will be equal to twice the treatment effect. Physical exam and EKG will be descriptive between the two groups (treatment vs. placebo). More complex situations, including testing for treatment \* order interaction, can be analyzed with longitudinal regression models.

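### Stage 2's first primary safety measure compares adverse events by dose level reached, and no whole-phase comparison by assigned treatment is committed

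*Combined protocol and SAP*

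**What the plan says.** The measure appears twice. Section IV.A (Stage 2, Primary Outcome Measures, item 1) has "By examining and comparing the frequency of study-related adverse events at each dose level between the two groups (treatment vs. placebo". Section IV.F (Stage 2, primary item 1) repeats it as "frequency of study-related adverse events at each dose level in the two groups, treatment vs. placebo", mostly descriptive, with proportions and confidence intervals.

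What is randomised is the order of treatments. Section C.5 has "Equal numbers from each block will be assigned to each of two sequence groups".

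Dose level is not randomised. Under Dose escalation strategy in C.3, each phase starts at 5 mg/kg/day for 10-15 days. The dose then rises every 3 days as tolerated, until the subject reaches the target or "experiences intolerable adverse effects, in which case the dose will be dropped to the last tolerated dose". The maximal tolerated dose is the one for which the next step up failed in two attempts. It is then held for 28 +/-4 days, although the opening text of C.3 gives 10-15 days for a subject who does not reach 20 mg/kg/day.

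Other text bears on the point:
- Section F: "Intention to treat concept is followed".
- Stage 2 introduction in F: "the analysis will be performed in accordance with the analysis plan devised prior to unblinding", and outcomes "will be analyzed as below for both the low dose (5 mg/kg/day) and highest tolerated dose".
- Item 1 in F: "Proportions, logistic regression, and relative risk regression can be applied to binary outcomes over a fixed period of time", with Poisson models offered in the same permissive way.
- Item 4 in F compares dropout for intolerance. C.7 tabulates withdrawals and discontinuations by treatment.

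None of these fixes an adverse-event period covering the whole phase or counts subjects who only reduce dose.

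**The concern.** Under this measure the outcome helps to choose its own denominator. A subject is counted at 15 or 20 mg/kg/day only after coping with the levels below. If CBD causes events in a sensitive minority, more of that minority leave the ladder early on CBD than on placebo. The groups compared at the higher levels then differ in more than treatment. Exposure differs as well: a subject passing through 10 or 15 mg/kg/day spends 3 days there, while one who is held there spends weeks.

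A contrast headed treatment against placebo will be read as randomised. Without days at risk per level and a committed whole-phase comparison, a reader cannot separate a drug effect at a dose from who reached that dose and how long they stayed.

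**Working it through.** **1. Which rows compare everyone.** Every subject who starts a phase takes 5 mg/kg/day for the first 10-15 days, so those days compare all starters. Later time at 5 mg/kg/day after a step-down does not, and neither does any higher level.

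**2. The plan's own figure.** There is none for this measure. The sample size of 38 concerns tremor (it reproduces with a paired t-test, power 0.902) and has no bearing here.

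**3. Illustration of selection at the top level.**

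Days at 5/10/15/20/25 mg/kg/day are 10/3/3/5/28, from C.3 and the Stage 2 schedule. Everything else is assumed:
- constant background rate *b*, giving a 55% placebo phase risk: *b* = -ln(0.45)/49 = 0.0163 per day (20% and 80% also tried);
- 30% of subjects sensitive, with added CBD risk *q* = 5/25/45/55/55% on entering each level;
- a share *f* of events is dose-limiting.

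Formulas: background risk at a level p0 = 1 - exp(-*b* x days); sensitive subjects on CBD p = 1 - (1 - p0)(1 - *q*).

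Results: p0 = 0.150/0.048/0.048/0.078/0.366; p = 0.193/0.286/0.476/0.585/0.715.

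If all were treated at 25, the excess would be 0.30 x (0.715 - 0.366) = 10.5 points.

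*One failed attempt ends escalation*, *f* = 0.5. Probability of reaching 25 = product of (1 - *f*p) over the four lower levels:
- sensitive: 0.904 x 0.857 x 0.762 x 0.707 = 0.417;
- others: 0.925 x 0.976 x 0.976 x 0.961 = 0.847;
- sensitive share among those at 25: 0.30 x 0.417 / (0.30 x 0.417 + 0.70 x 0.847) = 0.174;
- excess shown: 0.174 x 0.3485 = 6.1 points, or 58% of 10.5.

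*Two attempts failing independently.* Replace *f*p by (*f*p) squared and change nothing else:
- sensitive: 0.991 x 0.980 x 0.943 x 0.914 = 0.837; others 0.992;
- sensitive share at 25: 0.266;
- excess shown: 9.3 points, or 89%.

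Share of the top-level excess shown, over backgrounds of 20-80%:

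| Events dose-limiting | One attempt, or second always fails | Two independent attempts |
|---|---|---|
| 30% | about 75% | about 96% |
| 50% | about 58% | 87-90% |
| 100% | 23% | 51-59% |

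If 20 mg/kg/day is the top level (C.3 gives both 20 and 25), the one-attempt figures are about 85%, 74% and 48%. With equal susceptibility the share is 100% throughout.

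**4. Time at a level works the other way.** Add the chance of an event while held for *h* days after a step-down: (1 - p) x *f*p(next level) x (1 - exp(-*b* x *h*)). At 5 mg/kg/day, with *f* = 0.5, *h* = 28 and one attempt:
- sensitive: 0.193 + 0.807 x 0.143 x 0.366 = 0.235;
- others: 0.150 + 0.850 x 0.024 x 0.366 = 0.158;
- excess shown: 0.30 x (0.235 - 0.158) = 2.3 points, against 1.3 if all were treated.

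At 10 mg/kg/day the table shows 8.6 points with 28-day holds, or 7.7-8.0 with 10-15-day holds, against 7.1. With two independent attempts and 28-day holds these inflations shrink, to about 1.5 points at 5 and 7.6 at 10.

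**5. Precision of a whole-phase any-event proportion.** In this model escalation ends only after an event, so phase risk is 1 minus the product of (1 - risk) over levels. At 55% background this is 67.4% on CBD against 55.0%, an excess of 12.4 points. Assume 45 pairs (50 less 10% dropout) and treat the phases as independent. The half-width is 1.96 x sqrt((0.674 x 0.326 + 0.55 x 0.45)/45) = 20.0 points, and excess over standard error is 1.22. The by-level contrast at 15 mg/kg/day (one attempt, *f* = 0.5) gives 1.73. At 80% background the ratios are 0.70 and 1.34; at 20% they are 2.33 and 2.19.

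**The case against.** The strongest reply is that the plan's rule is milder than one strike. The maximal tolerated dose requires two failed attempts at the next level, so fewer sensitive subjects are lost. That stands, and it moves the illustration at half dose-limiting events from 58% to as high as 90%. Nothing in the documents says how closely the two attempts agree, so both ends remain possible.

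Second, the crossover helps. The plan allows McNemar's test, GEE or mixed models on repeated measures. A within-subject contrast at a level reached in both phases answers a fair question about people who can take that dose. This stands in part: the contrast is optional, and it leaves out those who could not tolerate that level on CBD.

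Third, an any-event whole-phase proportion can be noisier than a by-level contrast, as step 5 shows. This also stands, so it should not be the only whole-phase measure.

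Fourth, some cover exists already. Proportions with confidence intervals imply a denominator at each level. Events above the highest tolerated dose are still counted at the level where they occurred, although an analysis at the highest tolerated dose, read literally, omits them. Intention to treat, the plan fixed before unblinding, and the dropout and withdrawal tables all help. What remains is that permissive wording commits to no whole-phase event comparison, and that dose reductions go uncounted.

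**Conclusion.** The point holds as a gap in how the first primary safety measure is defined. By-level contrasts are conditioned on earlier events and on unequal time, and no whole-phase event comparison by assigned treatment is committed.

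The size is not known. The 58% and 87-90% figures rest on assumed event rates, a 30% sensitive share and half of events being dose-limiting. The two-attempt version also ignores the extra time that a second attempt takes.

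A reader might infer three stronger things, which the documents do not support:
- *That the table will hide most of the harm at the top dose.* In the illustration this needs every event to be dose-limiting and a second attempt that adds nothing. With equal susceptibility there is no selection bias at all.
- *That no primary measure is compared over the phase by treatment.* Dropout for intolerance is; the gap concerns event frequency.
- *That the 5 mg/kg/day row is clean.* Only its initial 10-15 days are.

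The measure is mostly descriptive and no sample size rests on it. This is a worthwhile, inexpensive improvement to the primary safety report.

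**What to change.** In IV.A (Stage 2, item 1) and IV.F (Stage 2, primary item 1), commit to a whole-phase comparison alongside the by-level tables. Compare by the treatment assigned in that phase, for all subjects dosed in it whatever dose they reached, within subject and with a period term. Report the following for study-related and for all-cause events:
- the event rate, by Poisson model with days on treatment as offset;
- the proportion with at least one event of moderate or worse severity, on the C.8 scale;
- the proportion with any event.

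Keep the by-level tables as descriptive. Label everything except the initial days at 5 mg/kg/day as non-randomised. Show subjects at risk, days at risk and dose reductions per level by treatment. A within-subject contrast at levels reached in both phases may be added, described as applying to subjects who tolerate that level.

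The sponsor must reconcile the two hold lengths in C.3 (28 +/-4 days and 10-15 days), because days at risk depend on them. No dosing rule changes.

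The cost is wording in two places and one added table. Events are recorded from the first dose (Stage 2 schedule, note b), severity is on the adverse-event page, and the diary records dose instructions. The downside is that any-event proportions lose contrast when background events are common. That is plausible here: the phone script solicits events by yes/no questions, and C.1 cites events in 79% on drug in a different population. This is why the any-event proportion should not stand alone.
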